# 5.3. Data Analysis

#### General

The data for analytic variables will be examined to identify unusual values, patterns of missing values and whether their distributions are non-Gaussian (i.e., have significant skewness and kurtosis). Data from variables with non-Gaussian distributions will be transformed, if necessary, before building statistical models. Missing data patterns will be examined and, when necessary for the data analysis, missing data may be imputed by appropriate methods depending on the pattern and mechanism of the missing data. Descriptive statistics (means, SD, and percentages with appropriate one-sided confidence intervals [CI]) and graphical displays (histograms, scatterplots, Kaplan-Meier curves) will be used to summarize study variables.

# Aim 1: To determine the feasibility, acceptability, tolerability and safety profile of IVIG treatment after HPE for biliary atresia.

**Hypothesis 1:** Administering IVIG will be feasible, acceptable and well tolerated in infants with BA without significant toxicity.

The percentage of subjects (and one-sided 90% Clopper-Pearson lower confidence bounds) in which the study is feasible and acceptable will be calculated. Point estimates and one-sided 90% Clopper-Pearson lower confidence bounds will be calculated for safety and tolerability parameters.

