#### 4.3.1. **Primary Outcome Measures**:

- 1. Feasibility: Percentage of subjects for whom administration of IVIG is feasible, defined as the successful administration (at least 80% of each dose) of the 3 doses of IVIG at the prescribed times through peripheral IV lines or central lines if already in place for clinical indications.
- 2. Acceptability: Percentage of subjects for whom the study is acceptable, defined as the ability of the subject's family or guardian to allow intravenous line placements, blood draws, and other study procedures for the study subjects.
- 3. Safety and tolerability measures:
  - a. Percentage of subjects with any serious adverse events (SAEs),
  - b. Percentage of subjects with any level 3, 4, or 5 toxicity (per NCI CTEP grading system [http://www.eortc.be/services/doc/ctc/ctcaev3.pdf], and
  - c. Percentage of subjects with other expected adverse events (such as allergic reactions, irritability, fluid volume problems, IV infiltration and aseptic meningitis).

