#### 5.2.1. Feasibility, Acceptability, Tolerability and Safety

To determine the feasibility, acceptability, tolerability and safety profile of IVIG treatment after HPE for BA (Aim 1), we will determine the proportion of participants who have feasibility, acceptability, tolerability and safety problems with IVIG treatment. For convenience below, we discuss power and precision in terms of adverse events (reflecting the focus on safety), although the same considerations apply to each of feasibility, acceptability, and tolerability. We anticipate that 23-29 subjects will receive IVIG. With this number of treated subjects, we have greater than 98% power to observe at least one subject with a specific adverse event when the true event rate is 20%, 91 to 95% power to observe at least one subject with a specific adverse event when the true event rate is 10%, and 69 to 77% power to observe at least one subject with a specific adverse event when the true event rate is 5%, based on calculations from the binomial distribution.

The power to reject the null hypothesis that the proportion of subjects with either a specific adverse event or any adverse event is 40% or higher, if the true proportion is 10%, 20% or 30% and using a one-sided 10% Type I error rate is provided in Figure 4. With 23 treated subjects, there is 70% power to detect a 40% or higher proportion if the true proportion is 20%, and 79% power to detect this difference with 29 treated patients (exact one-sample binomial test, SAS 9.3). These considerations also apply to the other outcomes described in Aim 1 – feasibility, acceptability and tolerability.

**Figure 4.** Power to Detect Proportion of Outcomes  $\geq$  40%, if the True Proportion is 10%, 20%, or 30% for Various Sample Sizes and one-sided Type I error of 10%

It is important to note that the level used for the null hypothesis in these calculations (40% or higher) is arbitrary and used for purposes of illustration only. Depending on the nature of the adverse event, a much higher rate might well be acceptable if the event is relatively minor and there is clear benefit in terms of lower serum bilirubin or higher survival without liver transplantation, while a much lower rate of a very serious and unusual adverse event might be unacceptable even in the presence of higher survival without liver transplantation.

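### Section 5.3 puts one-sided lower confidence bounds on adverse-event percentages, so the planned interval cannot exclude a high event rate and runs opposite to the test powered in Section 5.2.1

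*Protocol*

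**What the plan says.** Section 5.3, Aim 1, sets the interval for each group of primary outcomes. For feasibility and acceptability: "The percentage of subjects (and one-sided 90% Clopper-Pearson lower confidence bounds) in which the study is feasible and acceptable will be calculated". For safety and tolerability: "Point estimates and one-sided 90% Clopper-Pearson lower confidence bounds will be calculated for safety and tolerability parameters". Both groups get the same side.

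Section 4.3.1 defines the safety and tolerability measures as event percentages. Item 3a is "Percentage of subjects with any serious adverse events (SAEs", and item 3b is "Percentage of subjects with any level 3, 4, or 5 toxicity". Item 3c is the percentage with other expected adverse events.

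The hypothesis behind the aim is "Administering IVIG will be feasible, acceptable and well tolerated in infants with BA without significant toxicity".

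In Section 5.2.1 the hypothesis to be rejected is "the proportion of subjects with either a specific adverse event or any adverse event is 40% or higher", with power evaluated "if the true proportion is 10%, 20% or 30% and using a one-sided 10% Type I error rate". For a true proportion of 20% it states 70% power with 23 treated infants and 79% with 29, by an exact one-sample binomial test. It adds that the 40% level is arbitrary and illustrative.

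No part of the protocol plans an upper bound for an adverse-event rate. The general paragraph of Section 5.3 asks only for appropriate one-sided intervals.

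**The concern.** A one-sided bound should limit the parameter on the side that matters for the claim. For feasibility and acceptability, success means a high percentage, so a lower bound is right. For the percentage of infants with a serious adverse event or a grade 3 to 5 toxicity, the claim is that the percentage is not too high, and only an upper bound speaks to that. The lower-bound wording fits the first group and appears to have been carried over to the second.

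Safety is a primary outcome in a trial that, by Section 3, has no published or clinical experience of IVIG in these infants after HPE to draw on. Its results are meant to inform whether a larger trial is worth doing (Section 2.4). If the plan is followed literally, the prespecified interval for that outcome says only how low the event rate could be. An upper bound added after the data are seen would be an unplanned change to a primary analysis.

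**Working it through.** **Inputs.** n = 23 to 29 treated infants (Section 5.2.1: "We anticipate that 23-29 subjects will receive IVIG"); null event rate 40% or higher; true rate 20%; one-sided type I error 10% (Section 5.2.1); one-sided 90% Clopper-Pearson bounds (Section 5.3).

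**Step 1: reproduce the stated power.** The exact test of a rate of 40% or higher rejects when the number of events X is at most c, where c is the largest integer with P(X ≤ c | n, 0.40) ≤ 0.10. Power is P(X ≤ c | n, 0.20).

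- n = 23: c = 5. P(X ≤ 5 | 0.40) = 0.054, and P(X ≤ 6 | 0.40) = 0.124 is too large. Power = P(X ≤ 5 | 0.20) = 0.695, against a stated 70%.
- n = 29: c = 7. P(X ≤ 7 | 0.40) = 0.057, and P(X ≤ 8 | 0.40) = 0.119 is too large. Power = P(X ≤ 7 | 0.20) = 0.790, against a stated 79%.

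Both figures reproduce. The powered inference is therefore that few events show the rate to be below 40%.

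**Step 2: compare the two bounds.** With x events in n infants:

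- lower = 10th percentile of Beta(x, n − x + 1), and 0 when x = 0
- upper = 90th percentile of Beta(x + 1, n − x)

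| Events | Observed | Planned lower bound | Upper bound |
|---|---|---|---|
| 0/23 | 0% | 0% | 9.5% |
| 5/23 | 21.7% | 11.0% | 36.6% |
| 6/23 | 26.1% | 14.3% | 41.3% |
| 0/29 | 0% | 0% | 7.6% |
| 3/29 | 10.3% | 3.9% | 21.6% |
| 7/29 | 24.1% | 14.0% | 37.2% |
| 8/29 | 27.6% | 16.8% | 40.9% |
| 12/29 | 41.4% | 28.8% | 55.0% |

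The upper bound falls below 40% at exactly the counts from Step 1: at most 5 of 23 and at most 7 of 29. An interval reported on that side would match the powered test.

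**Step 3: what the planned lower bound can show.** It can only show that a rate is too high. It exceeds 40% from 13/23 (41.1%) or 16/29 (41.7%) upward; at 15/29, with 51.7% of infants affected, it is still 38.4%. If the true rate is 20%, the probability of reaching those counts is about 0.0001 (n = 23) or 0.00003 (n = 29). The 70% and 79% in Section 5.2.1 therefore do not describe anything the planned bound delivers. At zero events the lower bound is 0 by construction and adds nothing to the point estimate.

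**The case against.** The strongest case on the other side is that the slip does little harm.

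- The same sentence plans point estimates, and the aim is to describe a safety profile. Anyone with the count and n can compute the upper bound. This stands. A reader might infer that the primary safety question cannot be answered, or that only the favourable side would be shown; the documents do not support either. At 12/29, for example, the report would give 41.4% beside the 28.8% bound.
- A lower bound does exclude something, namely rates below it, and at 16/29 it would show a rate above 40%. This also stands, so it would be wrong to say that no rate can be excluded. What cannot be excluded is a high rate.
- Section 5.2.1 calls the 40% level arbitrary and says tolerable rates depend on the event. Section 5.3 plans no formal test for Aim 1. So no acceptance limit or decision rule is broken. The direction of the bound, however, does not depend on the threshold: a lower bound excludes no ceiling, whatever the level chosen. The other sizing basis in Section 5.2.1, the chance of seeing at least one event, is untouched.
- The stopping criteria (Section 7.5) and the rules for discontinuing IVIG in a subject (Sections 4.4.5 and 4.12.3) do not use the bound. This stands; monitoring of subjects is not affected.
- The general paragraph of Section 5.3 asks for appropriate one-sided intervals. That gives an analyst some ground for correcting the side, but it does not override the Aim 1 text, which names the side explicitly. A separate analysis plan that follows the protocol would inherit the error.

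A lower bound would fit if the parameters were percentages free of events, but Section 4.3.1 does not define them so.

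**Conclusion.** Wrong as written; should be fixed. The bound named in Section 5.3 for safety and tolerability is on the wrong side for outcomes defined as percentages with events. It cannot support the no-significant-toxicity part of Hypothesis 1, and it is opposite in direction to the test powered in Section 5.2.1. In size, the planned interval always extends to 100%, whereas the correct side would give a ceiling of 7.6% at 0/29, 21.6% at 3/29 and 37.2% at 7/29.

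The conclusion rests on the outcome definitions in Section 4.3.1 and on 23 to 29 treated infants. It does not rest on 40% as an acceptance limit, which the protocol does not set. The fault lies in the reporting rule and does not extend to the data, the sample size, the point estimates or the stopping criteria.

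**What to change.** In Section 5.3, Aim 1, keep the one-sided 90% lower bounds for feasibility and acceptability. For outcomes 3a to 3c of Section 4.3.1, replace the lower bound with a one-sided 90% Clopper-Pearson upper bound. A two-sided 80% interval would also serve, since its upper limit is the same one-sided 90% bound.

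Optionally, add to Section 5.2.1 a line on the precision the trial offers, such as the upper bounds at 0, 3 and 7 events of 29.

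The cost is a change of wording in one sentence, with no change to data collection, sample size or conduct. It is best made before the safety data are analysed, so that the upper bound is prespecified.

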# Aim 2: To obtain preliminary evidence whether IVIG therapy is associated with lower serum bilirubin concentration after HPE.

*Hypothesis 2a*: The probability of an infant having good bile drainage at 90 and 180 days after HPE (as defined by survival 90 or 180 days after HPE with both their native liver and serum total bilirubin level <1.5 mg/dL at 90 or 180 days after

HPE) will be greater in infants who are treated with IVIG compared to historical controls.

The proportions of subjects who have survived with their native liver and have bilirubin <1.5 mg/dL will be calculated at both time points. Each proportion will be compared to that of historical controls from the placebo group in the START study using Fisher's exact test. Given that previous studies have found age at HPE to be predictive of later clinical outcomes, we will perform an exploratory logistic regression analysis, including IVIG treatment (vs control) and age at HPE as covariates. Odds ratios and one-sided 90% Wald upper confidence bounds will be presented.

*Hypothesis 2b*: The probability of an infant having good bile drainage at 360 days after HPE (as defined by survival 360 days after HPE with both their native liver and serum total bilirubin level <1.5 mg/dL at 360 days after HPE) will be greater in infants who are treated with IVIG compared to historical controls.

The same methods will employed as in Hypothesis 2a.

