### 4.2.2. Exclusion criteria

- Laparoscopic HPE or "gall bladder Kasai" (cholecysto-portostomy) surgery was performed
- Biliary atresia splenic malformation syndrome (presence of asplenia, polysplenia or double spleen)
- History of a hypercoagulable disorder
- Renal Disease defined as serum creatinine > 1.0 mg/dl prior to enrollment or presence of complex renal anomalies found on imaging
- Evidence of congestive heart failure or fluid overload
- Presence of significant systemic hypertension for age (defined as persistent systolic blood pressure ≥112 mmHg measured on at least 3 occasions following HPE)
- Infants whose mother is known to have human immunodeficiency virus infection
- Infants whose mother is known to be serum HBsAg or hepatitis C virus antibody positive
- Previous treatment with intravenous immunoglobulin therapy for any reason
- Previous treatment with corticosteroid therapy for post-operative treatment of biliary atresia
- Previous treatment with any other investigational agent
- History of allergic reaction to any human blood product infusion
- Infants with other severe concurrent illnesses, such as neurological, cardiovascular, pulmonary, metabolic, endocrine, and renal disorders, that would interfere with the conduct and results of the study
- Any other clinical condition that is a contraindication to the use of IVIG

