# 5.2.2. Preliminary Efficacy (Activity).

The use of concurrent placebo or active control subjects was considered for this study, however it is not feasible to treat infants in a research study with an IV placebo (normal saline) and the availability of robust patient-level data for historical controls from another ChiLDREN study were felt to justify the bias issues inherent in the use of historical controls.

Placebo subjects from the ChiLDREN START (Steroids in Biliary Atresia Randomized Trial) study will be used as a historical comparative group to compare with subjects in this study who receive IVIG. Approximately 70 subjects in START received placebo from 2006-2011, but were otherwise treated similarly to the subjects in the current trial, except they received no IVIG. It is anticipated that the START randomized double-blind study will be unblinded in early 2013. With the anticipated length of this IVIG study (24-30 months enrollment and 12 months of follow-up), we will be able to use the START placebo subjects as the comparative group.

A one-sided testing strategy was chosen given that we are only interested if IVIG improves the preliminary measures of efficacy.

Hypothesis 2a states that treatment with IVIG will improve the probability of an infant having good bile flow 90 and 180 days after HPE for BA as evidenced by total serum bilirubin concentration. The primary endpoint for this hypothesis is the proportion of subjects who survive 180 days after HPE with both their native liver and serum total bilirubin <1.5 mg/dL at 180 days after HPE. Based on the ChiLDREN PROBE prospective study, approximately 51% of BA subjects who had an HPE before 4 months of age had good bile drainage at 6 months following the HPE procedure, as determined by a serum total bilirubin level <1.5 mg/dL and survival with their native liver. We anticipate the same improvement in the placebo subjects in the ChiLDREN START study.

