# Aim 3: To obtain preliminary evidence whether IVIG treatment after HPE will improve survival without liver transplantation at 360 days after HPE.

**Hypothesis 3:** Survival without transplantation will be greater at 360 days after HPE in infants treated with IVIG compared to historical controls.

The proportion of subjects who have survived with their native liver at 360 days after HPE will be estimated among the IVIG treated subjects and the historical placebo controls by Kaplan-Meier methods. Time to liver transplantation or death will be calculated as the number of days from the day of HPE to the first of liver transplantation, death, or last day of follow-up without these events. Subjects will be censored if these events don't occur by the last day of study follow-up. The difference between the two Kaplan-Meier estimates will be computed and a 90% upper confidence bound will be calculated for the difference, using the pooled variance (based on each group's standard error calculated with Greenwood's formula).

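### The stated comparisons with START placebo controls for Aims 2 and 3 are unadjusted, although the protocol names age at HPE as a predictor of outcome

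*Protocol*

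**What the plan says.** **Aim 2 (section 5.3).** For Hypothesis 2a, at 90 and 180 days: "Each proportion will be compared to that of historical controls from the placebo group in the START study using" Fisher's exact test. Adjustment follows as a second step: "Given that previous studies have found age at HPE to be predictive of later clinical outcomes, we will perform an exploratory logistic regression analysis". Apart from treatment, age at HPE is the only covariate in that model. For Hypothesis 2b, at 360 days: "The same methods will employed as in Hypothesis 2a".

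**Aim 3 (section 5.3).** Survival with native liver at 360 days is estimated by Kaplan-Meier in each group. Then: "The difference between the two Kaplan-Meier estimates will be computed and a 90% upper confidence bound will be calculated for the difference". No covariate, matching or weighting is mentioned.

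**Controls (section 5.2.2).** The comparator is the placebo group of the network's earlier steroid trial: "Approximately 70 subjects in START received placebo from 2006-2011, but were otherwise treated similarly to the subjects in the current trial", apart from the IVIG. The section concedes that historical controls bring bias and justifies them by the patient-level data available. Section 5.2 calls the controls a comparable population. No rule is stated for selecting them by this trial's own criteria (sections 4.2.1 and 4.2.2), which exclude, for example, infants with splenic malformation syndrome.

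**The concern.** Without randomisation, nothing makes the two groups alike in prognosis. The protocol names one predictor of outcome, age at HPE, and says that patient-level control data exist. Both ingredients for adjustment are therefore at hand, but the comparison it designates does not use them. If the IVIG infants had their HPE at a prognostically better or worse age than the START infants, that difference enters the Fisher p-value and the Kaplan-Meier difference as if it were due to the drug. For Aim 2 the reader would have an exploratory model to set beside the crude result. For Aim 3 there would be nothing.

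Sections 2.4 and 6.4 say that the combined findings should help determine whether a larger phase 2 or 3 trial is entertained. A biased activity signal would be one part of that judgement.

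**Working it through.** **Inputs (section 5.2.2).** One-sided 10% Fisher's exact test. Group sizes 23 and 56 after 20% loss, or 29 and 70 without loss. Success at 180 days 51% in controls and 76.5% on IVIG.

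**Formula.** With n1 IVIG infants and n2 controls, x and y successes, and true rates p1 and p2, the rejection probability is the sum of Bin(x; n1, p1) × Bin(y; n2, p2) over all (x, y) whose one-sided hypergeometric p-value is at most 0.10.

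**Step 1: reproduce the plan's power.** For 76.5% versus 51%:

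| n1 / n2 | Stated | Recomputed |
|---|---|---|
| 23 / 56 | 74% | 74.3% |
| 29 / 70 | 82% | 82.2% |

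The plan's figures are right, and the enumeration matches its method.

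**Step 2: no drug effect, groups differing in background success.** Controls are held at 51%. The IVIG group's background rate is 51% plus a shift. The shifts are assumptions.

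| Shift in IVIG background rate | 23 / 56 | 29 / 70 |
|---|---|---|
| -10 points | 1.0% | 0.8% |
| -5 points | 2.7% | 2.6% |
| none | 6.3% | 6.7% |
| +5 points | 13.0% | 14.7% |
| +10 points | 23.7% | 27.6% |

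Keeping IVIG at 51% and lowering the control rate instead gives nearly the same: 13.2% and 15.0% for 5 points, 24.1% and 28.3% for 10 points.

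**Step 3: a real effect hidden.** If an unfavourable 10-point shift takes the IVIG rate from 76.5% to 66.5%, power falls from 74% to 40% (23/56) and from 82% to 47% (29/70).

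**Step 4: does adjustment help, and does it cost power?** Simulation, 2,000 runs per setting. Model: logit(success) = b0 + effect × IVIG + beta × z, where z is age at HPE in SD units, signed so that higher is more favourable. Assumptions: beta 0.5 to 0.8, control success 51%, IVIG infants 0 to 0.5 SD more favourable. A 0.5 SD imbalance puts the IVIG background rate at 56.9% to 59.7%, about 6 to 9 points above 51%.

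Rejection rate with no drug effect, over both pairs of sample sizes:

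| Age imbalance | Fisher, unadjusted | Logistic, age-adjusted |
|---|---|---|
| none | 6-7% | about 10% |
| 0.25 SD | 10-13% | 9-11% |
| 0.5 SD | 15-26% | 10-12% |

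With no imbalance and a true IVIG rate of about 76-77%, power is 83-84% adjusted against 73-76% for Fisher (23/56), and 89-90% against 81-83% (29/70). Part of that gain arises because Fisher's actual size is below 10%. Adjustment cost no power in these settings.

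**Step 5: cost of restricting controls.** If an assumed 20% of the 56 controls were removed, about 45 would remain, and Fisher power for 76.5% versus 51% would fall from 74.3% to 70.8%.

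**The case against.** These aims are secondary and seek preliminary evidence; the trial is sized mainly on feasibility, tolerability and safety. The protocol admits the bias of historical controls, and it does prespecify an adjustment for the one predictor it names: "we will perform an exploratory logistic regression analysis, including IVIG treatment (vs control) and age at HPE as covariates". The groups come from one network with shared care guidelines. All of this stands and limits the severity. It does not settle the point, because the protocol itself fixes which analysis is the comparison and which is exploratory, and gives Aim 3 no adjusted analysis. A SAP that followed this text would do the same.

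A reader might infer more than the document supports:

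- *That the bias would favour IVIG.* No START baseline data are given. The imbalance could equally hide an effect, and the shifts above are illustrations.
- *That ineligible infants are certain to be among the controls.* No filter is stated, and the power calculation starts from the whole placebo group. But START's criteria are not shown and may match this trial's, including its exclusion of "Biliary atresia splenic malformation syndrome (presence of asplenia, polysplenia or double spleen").
- *That Fisher's test is itself a fault because its size is 6-7% rather than 10%.* It is a valid test and its stated power is correct. A less conservative exact test would do nothing about confounding: under shifts of 5, 10 and 15 points favouring IVIG, Boschloo's test at 23/56 would reject 19%, 32% and 47% of the time, against 13%, 24% and 39% for Fisher's.
- *That the activity result alone decides on a further trial.* Sections 2.4 and 6.4 refer to the combined findings.

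**Conclusion.** The point holds as a weakness in the order of the analyses, not as an error of calculation. For a non-randomised comparison with a predictor already named and patient-level data said to be available, the adjusted estimate should lead, and Aim 3 needs one as well. The size depends on an unknown imbalance. The 13-28% and 1-3% rejection rates assume no drug effect, 51% control success and a 5 to 10 point difference in background success; the adjusted results also assume the stated strength of the age effect and a correctly specified model. Adjustment removes bias from age at HPE only. It does not remove differences of era or from unmeasured factors.

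**What to change.** In section 5.3:

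1. For Hypotheses 2a and 2b, make the logistic regression with treatment and continuous age at HPE the main analysis. Report a standardised risk difference (IVIG minus control) with its one-sided 90% lower bound. Keep Fisher's test as supportive.
2. For Aim 3, add an age-adjusted analysis, for example a weighted Kaplan-Meier difference or a Cox model.
3. Allow at most one further covariate, such as baseline total bilirubin, and only if START recorded it; the protocol documents its collection for this trial only.
4. State that where START's criteria were wider than sections 4.2.1 and 4.2.2, controls are restricted to infants who meet this trial's criteria, as far as START recorded them.

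The cost is wording and a little analysis work, with no new patients, visits or samples. There are two limits. With 23 treated infants and 76.5% success, only about 5 IVIG failures are expected (23 × 0.235 = 5.4; 29 × 0.235 = 6.8), so the model must stay small. Restriction may also leave fewer controls, with a loss of about 3 to 4 points of power if 45 remain instead of 56.

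### The one-sided bounds for the Aim 2 odds ratios and the Aim 3 survival difference are upper bounds, which on the natural reading cannot support the hypothesised benefit of IVIG

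*Protocol*

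**What the plan says.** Section 5.2.2 explains the sidedness: "A one-sided testing strategy was chosen given that we are only interested if IVIG improves the preliminary measures of efficacy". The power figures there use a one-sided 10% error rate.

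Section 5.3, Aim 2, repeats that the probability of good drainage "will be greater in infants who are treated with IVIG compared to historical controls". The main analysis is stated as "Each proportion will be compared to that of historical controls from the placebo group in the START study using Fisher's exact test". An exploratory logistic regression follows, "including IVIG treatment (vs control) and age at HPE as covariates", and for it "Odds ratios and one-sided 90% Wald upper confidence bounds will be presented". Hypothesis 2b uses the same methods.

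Section 5.3, Aim 3, states the hypothesis as "Survival without transplantation will be greater at 360 days after HPE in infants treated with IVIG compared to historical controls". Native-liver survival at 360 days is estimated in each group by Kaplan-Meier, and "a 90% upper confidence bound will be calculated for the difference, using the pooled variance". The Aim 3 paragraph names no hypothesis test.

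Neither paragraph says which outcome level is the modelled event, or in which order the Kaplan-Meier estimates are subtracted.

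**The concern.** With success as the event and IVIG compared with control, benefit is an odds ratio above 1 or a difference above 0. A one-sided 10% claim of improvement is then the statement that the 90% *lower* bound lies above 1 or above 0. The upper bound answers a different question: how large the benefit could be or, if it falls below the null value, whether IVIG is worse. Section 5.2.2 sets that second question aside.

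At stake is whether the reported bounds address the hypotheses at all. In Aim 3 the upper bound is the only inference that the analysis paragraph states, so followed literally it gives no statement in the direction of Hypothesis 3. In Aim 2 the age-adjusted model is the only analysis in that paragraph that allows for a prognostic difference from the historical controls, and its bound faces the same wrong way.

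**Working it through.** **Inputs.** All from Section 5.2.2: one-sided error 10%; 23 IVIG and 56 control subjects after 20% loss, or 29 and 70 without loss; good drainage at 180 days 76.5% versus 51%; at 360 days about 90% versus 68%. The 360-day power calculation is carried over to Hypothesis 3. z for a one-sided 90% bound is 1.2816.

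**Step 1: the plan's own figures and their direction.** Enumerating both binomials and rejecting when the one-sided Fisher p-value in favour of IVIG is at most 0.10:

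| Rates | Sizes | Stated power | Recomputed |
|---|---|---|---|
| 76.5% vs 51% | 23 / 56 | 74% | 74.3% |
| 76.5% vs 51% | 29 / 70 | 82% | 82.2% |
| 79% vs 51% | 23 / 56 | 80% | 81.6% |
| 79% vs 51% | 29 / 70 | 88% | 88.5% |
| 90% to 90.4% vs 68% | 23 / 56 | 76% | 74.5% to 76.4% |
| 90% to 90.4% vs 68% | 29 / 70 | 85% | 84.1% to 85.7% |

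The stated power figures agree to within 2 points, so the direction that was powered is IVIG better.

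**Step 2: Aim 2 bounds at the planning rates, 23 versus 56.** Expected cells: IVIG 17.595 successes and 5.405 failures; control 28.56 and 27.44.

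- OR = (17.595 × 27.44) / (5.405 × 28.56) = 3.13, log OR = 1.140
- SE = √(1/17.595 + 1/5.405 + 1/28.56 + 1/27.44) = √0.3133 = 0.560
- Lower bound = exp(1.140 − 1.2816 × 0.560) = 1.53
- Planned upper bound = exp(1.140 + 1.2816 × 0.560) = 6.41

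With 29 versus 70 the bounds are 1.65 and 5.93. These are unadjusted, because the protocol gives no age effect.

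**Step 3: Aim 3 bounds at the planning rates, 23 versus 56.** Without censoring, Greenwood's variance equals the binomial variance.

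- Difference (IVIG minus control) = 0.90 − 0.68 = +0.22
- SE = √(0.90 × 0.10/23 + 0.68 × 0.32/56) = √0.00780 = 0.0883
- Lower bound = 0.22 − 1.2816 × 0.0883 = +0.107
- Planned upper bound = 0.22 + 1.2816 × 0.0883 = +0.333

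With 29 versus 70 the bounds are +11.9 and +32.1 points.

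**Step 4: how often each bound excludes no effect if the planned effect is true (23 versus 56).**

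| | Lower bound above null | Upper bound below null |
|---|---|---|
| Aim 2 odds ratio, 76.5% vs 51% | 82% | 0.02% |
| Aim 3 difference, 90% vs 68% | 88% | 0.01% |

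**Step 5: what the upper bound can do.** If IVIG were harmful, with assumed rates of 25.5% versus 51%, the upper odds-ratio bound falls below 1 with probability 81% at 23 versus 56; with an assumed 38% versus 51% it is 42%. For null-like data of 15/29 versus 36/70 (an illustration), OR = (15 × 34)/(14 × 36) = 1.01 with upper bound 1.78, which excludes the planned odds ratio of 3.13.

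**Step 6: reverse coding.** If failure were the event, the upper odds-ratio bound at the planning rates would be 1/1.53, about 0.66 (computed from unrounded values). If the difference were control minus IVIG, its upper bound would be −10.7 points. Both would then show benefit.

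**The case against.** Five arguments can be made for the plan as written.

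- **Direction is not stated.** Under the reverse coding of Step 6 the upper bounds are right, and the Aim 3 time variable does run to transplantation or death. This stands as a limit on certainty. But Section 4.3.2 and both hypotheses are worded as successes, the model contrast is IVIG against control, and the quantity estimated in Aim 3 is survival with the native liver. Even on the reverse reading the direction has to be written down.
- **An upper bound is informative.** A reader might infer that the planned bounds can neither support nor refute benefit. The second half does not hold: Step 5 shows that they can contradict or cap a benefit.
- **Nothing is irretrievably lost.** Both bounds are symmetric, on the log scale or the difference scale, so the lower bound can be rebuilt from the point estimate: 3.13²/6.41 = 1.53, and 2 × 22 − 33.3 = +10.7. This is true, but a plan should report the bound that bears on its hypothesis.
- **Aim 2 has another test.** Fisher's exact test is the main comparison and the logistic model is labelled exploratory. This stands, and keeps the Aim 2 consequence small.
- **Aim 3 borrows the power of a Fisher test.** Section 5.2.2 applies the Hypothesis 2b calculation to Hypothesis 3, which suggests a one-sided comparison in favour of IVIG. The Aim 3 analysis paragraph does not carry that test over.

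Nor is this a detail left to a statistical analysis plan: the protocol itself fixes the side of the bound.

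**Conclusion.** The point holds on the natural reading: event is good drainage, contrast is IVIG versus control, difference is IVIG minus control. The planned bounds then lie on the wrong side for the stated hypotheses. At the planned effects with 23 versus 56 subjects, the plan would report 6.41 and +33.3 points where the bounds that bear on benefit are 1.53 and +10.7 points.

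The effect is greatest for Aim 3, where the bound is the only inference named in the analysis paragraph, and small for Aim 2. A reader might infer that the efficacy aims as a whole are left without valid inference; the documents do not support that, since the Fisher comparisons for Hypotheses 2a and 2b are unaffected and no sample-size or power figure depends on these two sentences. The aims are secondary and described as preliminary, so this should be fixed but is not critical.

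The figures assume no age adjustment, no censoring, a normal approximation for the Aim 3 bound, and the planning rates in Section 5.2.2.

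**What to change.** In Section 5.3, Aim 2, state that the modelled event is good drainage and that the odds ratio is IVIG versus control, and change the one-sided 90% bound from upper to lower. In Aim 3, state that the difference is native-liver survival on IVIG minus control, and make the same change. Alternatively, report two-sided 80% intervals in both places, as Aim 4 already does; their lower limits are the same one-sided 90% lower bounds, and the upper limits remain available.

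The cost is a wording change in two sentences. It needs no new data and leaves the sample size and the stated power unchanged.
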